3.1.2 Durvalumab monotherapy

Risks with durvalumab include, but are not limited to, diarrhea/colitis and intestinal perforation, pneumonitis/ILD, endocrinopathies (hypo- and hyper-thyroidism, type I diabetes mellitus, hypophysitis and adrenal insufficiency) hepatitis/increases in transaminases, nephritis/increases in creatinine, pancreatitis/increases in amylase and lipase, rash/pruritus/dermatitis, myocarditis, myositis/polymyositis, other rare or less frequent inflammatory events including neurotoxicities, infusion-related reactions, hypersensitivity reactions and infections/serious infections.

For information on all identified and potential risks with durvalumab please always refer to the current version of the durvalumab IB.

Further information on these risks can be found in the current version of the durvalumab IB.

In monotherapy clinical studies AEs (all grades) reported very commonly ($\geq 10\%$ of patients) are fatigue, nausea, decreased appetite, dyspnea, cough, constipation, diarrhea, vomiting, back pain, pyrexia, asthenia, anemia, arthralgia, peripheral edema, headache, rash, and pruritus. Approximately 9% of patients experienced an AE that resulted in permanent discontinuation of durvalumab and

approximately 6% of patients experienced an SAE that was considered to be related to durvalumab by the study investigator.

The majority of treatment-related AEs were manageable with dose delays, symptomatic treatment, and in the case of events suspected to have an immune basis, the use of established treatment guidelines for immune-mediated (Appendix 1).

A detailed summary of durvalumab monotherapy AE data can be found in the current version of the durvalumab IB.

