4 STUDY DESIGN

4.1 Description

This is a multi-center, open label phase II with safety run-in study. This study will assess the efficacy and safety of an aromatase inhibitor (anastrozole) in combination with durvalumab in patients with hormone-receptor-positive breast cancer. The objectives are to obtain data on the clinical efficacy and to assess the safety of the drug combination.

The study will test a fixed dose of durvalumab in combination with an AI. Initially, six patients will be enrolled in the safety run-in stage. If $\leq 1/6$ patients have a DLT, then the expansion stage will be open for enrollment. If $\geq 2/6$ patients have a DLT, we will amend the protocol.

Anastrozole 1 mg daily will be taken orally (PO) starting on Day 1 of each cycle for 6 months prior to definitive surgery. After the first 6 months, the patients will continue taking the AI at the discretion of the treating physician as per standard of care.

It is acceptable to switch to another AI (letrozole 2.5 mg or exemestane 25 mg daily) for intolerance such as hot flash or joint ache attributable to the AI). In the safety run-in phase, switching to another AI is allowed only after the post DLT period.

Table 4. Dosage for durvalumab and AI combination.

Durvalumab (IV)	AI (PO)
1500 mg Q4W on Day 1 of each 28-day cycles for 6 cycles	Anastrozole 1 mg (or letrozole 2.5 mg or exemestane 25 mg, if intolerance of anastrozole) for 6 months

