4.2 Dose Limiting Toxicity

Dose-limiting toxicities (DLTs) will be evaluated during the safety run-in phase of the trial. The period for evaluating DLTs will be the first cycle of treatment (from the time of first administration of durvalumab until the clinic evaluation prior to C2D1 dosing). Subjects who do not remain on the study up to this time for reasons other than DLT will be replaced with another subject. Grading of

DLTs will follow the guidelines provided in the Common Terminology Criteria for Adverse Events (CTCAE) version 5.0.

A DLT will be defined as any Grade 3 or higher toxicity that occurs during the DLT evaluation period and meets the criteria below. Toxicity that is clearly and directly related to the primary disease or to another etiology is excluded from this definition. The following will be DLTs:

- Any Grade 4 irAE (as defined in section 15.4.4 and 15.4.5).
- Any Grade ≥ 3 colitis.
- Any Grade ≥ 3 noninfectious pneumonitis irrespective of duration.
- Any Grade 2 pneumonitis that does not resolve to \leq Grade 1 within 3 days of the initiation of maximal supportive care.
- Any Grade 3 irAE, excluding colitis or pneumonitis, that does not downgrade to Grade 2 within 3 days of onset despite optimal medical management including systemic corticosteroids or does not downgrade to Grade ≤ 1 or baseline within 14 days.
- Liver transaminase elevation $> 8 \times$ ULN or total bilirubin $> 5 \times$ ULN.
- Grade 3 or 4 febrile neutropenia
- Any treatment interruption greater than 2 weeks due to an AE.
- Any \geq Grade 3 non-irAE, except for the exclusions listed below.

The definition excludes the following conditions:

- Grade 3 fatigue lasting ≤ 7 days.
- Grade 3 endocrine disorder (thyroid, pituitary, and/or adrenal insufficiency) that is managed with or without systemic corticosteroid therapy and/or hormone replacement therapy and the subject is asymptomatic.
- Grade 3 inflammatory reaction attributed to a local antitumor response (e.g., inflammatory reaction at sites of metastatic disease, lymph nodes, etc.).
- Concurrent vitiligo or alopecia of any AE grade.
- Grade 3 infusion-related reaction (first occurrence and in the absence of steroid prophylaxis) that resolves within 6 hours with appropriate clinical management.

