4.6 Withdrawal of Subjects from Study Treatment and/or Study

4.6.1 Permanent discontinuation of investigational product

An individual patient will not receive any further investigational product if any of the following occur in the patient in question:

1. An individual patient will not receive any further durvalumab if their weight falls to 30kg or less
2. Withdrawal of consent or lost to follow-up
3. Adverse event that, in the opinion of the investigator or the sponsor, contraindicates further dosing
4. Patient is determined to have met one or more of the exclusion criteria for study participation at study entry and continuing investigational therapy might constitute a safety risk
5. Any AE that meets criteria for discontinuation as defined in Section 10.3 and Appendix 1.
6. Dose-limiting toxicity (as defined in section 4.2)
7. Grade ≥ 3 infusion reaction
8. Patient noncompliance that, in the opinion of the investigator or sponsor, warrants withdrawal; e.g., refusal to adhere to scheduled visits
9. Initiation of alternative anticancer therapy including another investigational agent
10. Confirmation of PD and investigator determination that the patient is no longer benefiting from treatment with durvalumab
11. Subjects who are permanently discontinued from receiving investigational product will be followed for safety per Section 15.4 and Appendix 1, including the collection of any protocol-

specified blood specimens, unless consent is withdrawn or the subject is lost to follow-up or enrolled in another clinical study. All subjects will be followed for recurrence free survival. Subjects who decline to return to the site for evaluations will be offered follow-up by phone every 3 months as an alternative.

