7.1 Dose Modifications

7.1.1 Aromatase inhibitor

Dose modifications are allowed in case of toxicities thought to be related to the AI. Dose modifications will follow standard of care guidelines and will be at the discretion of the treating physician and Principal Investigator.

Switching to a different AI is permitted. In the safety run-in phase, switching is only allowed outside of the DLT window (details can be found in section 2.5.1).

Dose reductions in AI are not permitted but dose interruptions for up to 14 consecutive days for toxicity reasons is acceptable. Patients may continue to receive durvalumab per the dosing schedule if the toxicity is thought to be caused by the AI.

Patients who can't resume AI treatment after a 14 day hold will discontinue study treatment.

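### Section 4.2 does not clearly count as a DLT a confirmed cycle 1 Hy's law case that is Grade 2 on both liver measures

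*Combined protocol and SAP*

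**What the plan says.** - **Decision rule (Section 4.1).** Six patients enter the run-in. Expansion opens if at most one has a DLT. If two or more "patients have a DLT, we will amend the protocol".
- **Definition (Section 4.2, lead-in).** "A DLT will be defined as any Grade 3 or higher toxicity that occurs during the DLT evaluation period and meets the criteria below".
- **Window (Section 4.2).** From the first durvalumab administration "until the clinic evaluation prior to C2D1 dosing".
- **Criteria that could reach a liver event (Section 4.2).** Transaminases above 8 × ULN or bilirubin above 5 × ULN; a Grade 4 immune-related event; a Grade 3 immune-related event that fails a 3-day or 14-day downgrade test; any event of at least "Grade 3 non-irAE, except for the exclusions listed below"; and "Any treatment interruption greater than 2 weeks due to an AE".
- **Required action, Section 15.3.6.** With normal baseline values, AST or ALT above 3 × ULN together with bilirubin above 2 × ULN, without cholestasis, means immediate discontinuation. If repeat testing confirms it and no other cause is found, it is an SAE. No grade is mentioned.
- **Required action, Appendix (hepatitis).** Every case that fits Hy's law, at the same two thresholds, means permanent discontinuation. The line stands in the Grade 3 or 4 row.
- **Required action, Section 15.5.2.** Where no definite diagnosis explains the hepatic function abnormality (same thresholds, defined in Section 15.3.4), dosing is interrupted.

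**The concern.** The two-of-six rule is the only numerical safety gate before expansion. The plan treats a confirmed Hy's law pattern as reason to stop the drug at once, whatever the grade. Read literally, the DLT list can leave the same patient out of the count.

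The three action terms (discontinue, permanently discontinue, interrupt) make this worse, because the only criterion that might reach the patient turns on the word interruption. Two careful scorers could therefore record the same patient differently. That would change the decision when exactly one other DLT has been counted.

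**Working it through.** **1. Locate the liver zone.** The Appendix grades AST or ALT above 3 and up to 5 × ULN, and bilirubin above 1.5 and up to 3 × ULN, as Grade 2. Hy's law begins above 3 × and above 2 ×. The overlap is AST or ALT above 3 and up to 5 × ULN with bilirubin above 2 and up to 3 × ULN.

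| AST/ALT, bilirubin (× ULN) | Fits Hy's law | Grades | Section 4.2 liver bullet met |
|---|---|---|---|
| 4, 2.5 | yes | 2, 2 | no |
| 5, 3 | yes | 2, 2 | no |
| 6, 2.5 | yes | 3, 2 | no |
| 8.1, 2.1 | yes | 3, 2 | yes |

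The third row is already handled. If non-immune, it counts as a Grade 3 event; if immune-related, the downgrade rule decides. The gap is the Grade 2/Grade 2 zone. It is narrower for patients with raised baseline values, because Section 15.3.6 then also requires more than twice baseline.

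**2. Test that zone against Section 4.2.** The Grade 3 and Grade 4 criteria do not reach it, the liver bullet does not, and colitis, pneumonitis and febrile neutropenia are irrelevant. Only the interruption bullet remains, and three things leave it unclear:

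- The lead-in's Grade 3 floor stands over it. The Grade 2 pneumonitis bullet breaks the same floor, so a scorer must decide which text governs.
- It does not name a permanent stop. Section 15.3.1 records temporary interruption and permanent discontinuation as different actions.
- The first durvalumab dose that can be withheld is C2D1, day 29. A delay passes two weeks only after day 29 + 14 = 43, when the window has closed.

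**3. Size.** The plan states no operating characteristic for the run-in rule, so there is no figure to reproduce. Let c be the per-patient rate of counted DLTs and u the rate of Hy's law cases now left uncounted. Both are assumptions. With p = c + u once they count,

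P(expansion opens) = (1 − p)^6 + 6p(1 − p)^5.

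| c | u = 0 | u = 0.2% | u = 0.5% | u = 1% |
|---|---|---|---|---|
| 5% | 0.967 | 0.965 | 0.961 | 0.954 |
| 10% | 0.886 | 0.882 | 0.876 | 0.866 |
| 20% | 0.655 | 0.650 | 0.643 | 0.631 |

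Worked entry, c = 10% and u = 1%: 0.89^6 + 6 × 0.11 × 0.89^5 = 0.4970 + 0.3685 = 0.8655, a fall of 0.0202 from 0.8857. Of that fall, 6 × 0.10 × (0.90^5 − 0.89^5) = 0.0193 comes from run-ins with exactly one counted DLT.

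The chance that at least one of six patients has such a case is 1 − (1 − u)^6: 1.2%, 3.0% and 5.9% for u = 0.2%, 0.5% and 1%.

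The nearest documented rate is in Section 3.1.2: "Approximately 9% of patients experienced an AE that resulted in permanent discontinuation of durvalumab". It covers the whole course and every kind of AE, so it only gives scale: u = 1% is one ninth of it.

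**The case against.** The best defence is that the interruption bullet already covers the case. On its plain meaning, a permanent stop is treatment withheld for more than two weeks, and the bullet states no grade. Section 15.5.2 uses the word interrupted at these same liver thresholds. Section 7.1.1 draws the same line for the aromatase inhibitor (AI): patients who cannot "resume AI treatment after a 14 day hold will discontinue study treatment". The day-43 argument is also not decisive. Section 4.2 requires the toxicity to arise in the window, not every test to finish there; the 14-day downgrade test runs past C2D1 for any onset after day 15. And the AI is taken daily, so a stop of the whole regimen can exceed two weeks within cycle 1. This much stands: the plan does not clearly count the case, but a reader who infers that it definitely excludes it goes further than the text.

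A second objection is that the Appendix Hy's law line stands in the Grade 3 or 4 row, while the Grade 2 row says hold and then resume. The placement is awkward, but the line extends to every case at thresholds that are themselves Grade 2, and Section 15.3.6 does not depend on grade.

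A third objection concerns scope. A reader might infer that every stop the Appendix mandates should be a DLT, for example Grade 3 nephritis or myocarditis that downgrades quickly. The documents do not support that. Section 4.2 makes rapidly downgrading Grade 3 immune-related events non-DLTs by explicit rule. It also excludes a first Grade 3 infusion reaction that resolves within 6 hours, although Section 4.6.1 ends durvalumab for it. Section 4.6.1 lists "Any AE that meets criteria for discontinuation as defined in Section 10.3 and Appendix 1" and DLTs as separate items.

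**Conclusion.** The point holds in a narrow form: one well-defined liver event that requires the drug to be stopped is not clearly scored at the run-in gate. This is a matter of clear scoring, with a small numerical effect. At an assumed counted rate of 10% and an assumed 0.2% to 1% rate of such cases, counting them lowers the probability that expansion opens by 0.004 to 0.020. The documents give no cycle 1 rate for these events.

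A reader might also infer that a serious liver signal would go unseen. It would not. A confirmed case is an SAE, reportable within 24 hours under Section 15.4. Section 15.5.2 has its own 24-hour report. The Protocol Monitoring Committee reviews adverse events monthly and may stop the study (Section 16.2). None of these says how the patient enters the two-of-six count, and reaching two triggers an amendment rather than closure. The change is worth considering because it is cheap, not because the run-in is unsafe without it.

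**What to change.** Make two edits in Section 4.2.

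1. After the two existing limits in the liver bullet, add: *or any case confirmed as potential drug-induced liver injury or Hy's law (15.3.6, Appendix) with onset in the DLT window*.
2. Remove the grade floor from the lead-in, so that a DLT is any toxicity arising in the evaluation period that satisfies one of the listed criteria. This also removes the conflict with the Grade 2 pneumonitis bullet.

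Leave the attribution wording of the interruption bullet, the Grade 3 immune-related downgrade rule and the express exclusions unchanged, and do not turn every mandated stop into a DLT.

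Costs: the run-in rule becomes very slightly stricter, by the amounts given above. The added words would also count a confirmed Hy's law case that is a Grade 3 immune-related event and downgrades in time; the downgrade rule is otherwise untouched. Confirmation should not hold up scoring for long, since Section 15.3.6 asks for repeat tests preferably within 48 hours. With the floor gone, the interruption bullet plainly applies at any grade, including an AI hold of more than two weeks for a Grade 2 event. That is not in the figures, and the team should confirm it is intended. No patient's treatment rules change, except that under Section 4.6.1 an event newly scored as a DLT ends durvalumab; for the Hy's law case that stop is already required.

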4.3 Number of Patients

Safety run-in phase: 6 patients

Expansion phase: A total of 42 evaluable patients are required, when considering a rate of non-evaluability of 10%, a total of 46 patients are expected to enroll in the study (the 6 patients in the safety run-in phase are included in this total).

4.4 Number of Study Centers

The study will be conducted at two centers.

4.5 Duration

The total enrollment period for the study will be 28 months. Follow-up will be required for up to 5 years.

4.6 Withdrawal of Subjects from Study Treatment and/or Study

4.6.1 Permanent discontinuation of investigational product

An individual patient will not receive any further investigational product if any of the following occur in the patient in question:

1. An individual patient will not receive any further durvalumab if their weight falls to 30kg or less
2. Withdrawal of consent or lost to follow-up
3. Adverse event that, in the opinion of the investigator or the sponsor, contraindicates further dosing
4. Patient is determined to have met one or more of the exclusion criteria for study participation at study entry and continuing investigational therapy might constitute a safety risk
5. Any AE that meets criteria for discontinuation as defined in Section 10.3 and Appendix 1.
6. Dose-limiting toxicity (as defined in section 4.2)
7. Grade ≥ 3 infusion reaction
8. Patient noncompliance that, in the opinion of the investigator or sponsor, warrants withdrawal; e.g., refusal to adhere to scheduled visits
9. Initiation of alternative anticancer therapy including another investigational agent
10. Confirmation of PD and investigator determination that the patient is no longer benefiting from treatment with durvalumab
11. Subjects who are permanently discontinued from receiving investigational product will be followed for safety per Section 15.4 and Appendix 1, including the collection of any protocol-

specified blood specimens, unless consent is withdrawn or the subject is lost to follow-up or enrolled in another clinical study. All subjects will be followed for recurrence free survival. Subjects who decline to return to the site for evaluations will be offered follow-up by phone every 3 months as an alternative.

4.6.2 Withdrawal of consent

Patients are free to withdraw from the study at any time (from investigational product and assessments) without prejudice to further treatment.

Patients who withdraw consent for further participation in the study will not receive any further investigational product or further study observation, with the exception of follow-up for survival, which will continue until the end of the study unless the patient has expressly withdrawn their consent to survival follow-up. Note that the patient may be offered additional tests or tapering of treatment to withdraw safely.

A patient who withdraws consent will always be asked about the reason(s) for withdrawal and the presence of any AE. The Investigator will follow up AEs outside of the clinical study.

If a patient withdraws consent, they will be specifically asked if they are withdrawing consent to:

- all further participation in the study including any further follow up (e.g., survival contact telephone calls)
- withdrawal of consent to the use of their study generated data
- withdrawal to the use of any samples

4.6.3 Withdrawal of informed consent for donated biological samples

If a subject withdraws consent to the use of donated samples, the Principal Investigator will ensure that any stored samples are disposed of or destroyed, the action is documented, and the subject is notified of the samples' disposal. As collection of the biological samples is an integral part of the study, the subject will also be withdrawn from further study participation.

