- Serum bilirubin $\leq 1.5 \times$ institutional upper limit of normal (ULN). This will not apply to subjects with confirmed Gilbert's syndrome (persistent or recurrent hyperbilirubinemia that is predominantly unconjugated in the absence of hemolysis or hepatic pathology), who will be allowed only in consultation with their physician
- AST (SGOT)/ALT (SGPT) $\leq 2.5 \times$ institutional upper limit of normal.
- Serum creatinine clearance > 40 mL/min by the Cockcroft-Gault formula (1976) or by 24-hour urine collection for determination of creatinine clearance

_____ 5.1.10 Subjects must be willing to undergo a research biopsy at baseline and after one cycle of treatment and to provide tissue obtained at surgery for biomarker and correlative studies.

_____ 5.1.11 Subjects must be willing and able to comply with the protocol for the duration of the study including undergoing treatment and scheduled visits and examinations including follow up.

_____ 5.1.12 If taking herbal or natural remedies that may have immune modulatory effects, subjects must be willing to discontinue it prior to first dose of durvalumab.

_____ 5.1.13 Body weight > 30 kg.

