9.4.5 Correlative samples

Correlative blood samples

Blood samples for correlative studies will be collected for the following tests as well as stored for future research:

- Cytokine level measurement (before C1D1, C2D1, C4D1 and end of C6 or EOT).

Additional details about correlative blood samples are provided in section 14.4.

Archival tumor samples and fresh tumor biopsies

Tumor tissue samples will be collected before the first study treatment, at the end of cycle 1 (within 7 days), and from the definitive surgical specimens. Collection of fresh tissue samples may be omitted at the discretion of the PI.

Archival tissue is acceptable for enrollment after confirmation that stored tissue blocks are of adequate quality and can yield a minimum of 10 sections each 4 to 5 microns thick. A fresh biopsy is mandatory if the amount of archival tissue is insufficient.

Fresh tumor tissue collection via ultrasound-guided core biopsy is mandatory once a patient has completed one cycle of treatment (collection to be within 7 days of the end of a cycle). However, this may be omitted at the discretion of the PI.

Tumor tissue samples will be analyzed for changes in PD-L1 expression, changes in subtypes of immune infiltrates, cytokine patterns, and levels of Ki-67 expression.

Further details about sample collection, storage, and testing are provided in the laboratory manual and in sections 14.1 and 14.2.

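### Section 4.6.3 makes withdrawal of consent for research samples a withdrawal from the study, which before surgery causes avoidable missing mPEPI and unrecorded safety data

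*Combined protocol and SAP*

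**What the plan says.** **Sample withdrawal (4.6.3).** Stored samples are destroyed, the action is documented and the patient is told. The section then adds: "As collection of the biological samples is an integral part of the study, the subject will also be withdrawn from further study participation".

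**General withdrawal (4.6.2).** The section introduces three items with "If a patient withdraws consent, they will be specifically asked if they are withdrawing consent to". They are all further participation including follow-up, use of study data, and "withdrawal to the use of any samples". A patient who withdraws from participation receives no more study drug and is no longer observed under the study. The one carve-out is worded as "with the exception of follow-up for survival, which will continue until the end of the study unless the patient has expressly withdrawn their consent". On safety it says "The Investigator will follow up AEs outside of the clinical study".

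**Follow-up elsewhere.** Section 4.6.1, item 11, says "All subjects will be followed for recurrence free survival". The safety follow-up in the same item stops if consent is withdrawn. Section 10.2 has every patient followed through standard-of-care surgery for pathologic response.

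**Status of the samples.** Section 9.4.5 says "Collection of fresh tissue samples may be omitted at the discretion of the PI". Sections 9.1 and 9.2 and footnote 2 of the schedule in 8.2 give similar discretion over particular biopsies. On the other side, inclusion criterion 5.1.10 reads "Subjects must be willing to undergo a research biopsy at baseline and after one cycle of treatment and to provide tissue obtained at surgery", and footnote 2 makes tissue at definitive surgery mandatory.

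**The concern.** A patient may object only to research use of her tissue or blood and still be content to have surgery, report adverse events and be followed for recurrence. Under 4.6.3 she leaves the study anyway. The trigger is the use of donated samples, which includes stored ones. Sections 14.2 and 14.3 bank frozen tissue, serum and plasma for future work. On the wording, a patient in her third year who asks only for banked serum to be destroyed would leave a recurrence follow-up planned for up to 5 years (6.8; 8.2, footnote 17), although all sampling is over.

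Before surgery the stakes are higher. mPEPI is read from the surgical specimen (8.2, footnote 15), so the primary endpoint would not be collected under the study. Adverse events after a checkpoint inhibitor would be followed clinically but would not enter the trial's safety record. Section 4.7 does not replace expansion-phase patients. The efficacy set in 11.1.2 is defined by dosing, so she stays in it, and nothing says how her missing mPEPI is counted.

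**Working it through.** **1. What is lost, by timing.** Reading 4.6.3 with 4.6.1, 4.6.2, 15.3.1 and 15.3.2:

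| Item | Withdrawal before surgery | Withdrawal after surgery |
|---|---|---|
| mPEPI, pCR | not collected under the study | kept |
| AE/SAE to 90 days after last dose | remainder followed outside the study | same, if the window is still open |
| Recurrence | not observed under the study | not observed under the study |
| Survival | continues unless expressly withdrawn | continues unless expressly withdrawn |
| Data already recorded | kept | kept |

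**2. Reproducing the design (11.3).** Inputs: p0 = 0.10, p1 = 0.25, first stage 14, stop at 1 or fewer, final 42, success at 7 or more.

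- Early termination at p0: 0.9^14 + 14 × 0.1 × 0.9^13 = 0.2288 + 0.3559 = 0.585 (stated 0.585).
- Expected sample: 14 + (1 − 0.5846) × 28 = 25.63 (stated 25.63).
- Probability of success: sum over x = 2 to 14 of P(X1 = x) × P(X2 ≥ 7 − x), with X1 ~ Bin(14, p) and X2 ~ Bin(28, p). This gives 0.098 at p0 (limit 0.10) and 0.857 at p1 (target 0.85).

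The plan's figures are sound.

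**3. Room for losses.** 46 − 42 = 4 places, shared by all causes of non-evaluability. At the plan's own 10%, 0.10 × 46 = 4.6 losses are expected. Falling to 41 or 40 evaluable takes 5 or 6 losses in total.

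**4. Sensitivity.** The documents give no rate of sample-consent withdrawal, so all counts here are assumptions.

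(a) Lost patients are non-evaluable and the cut-off of 7 is kept. Replace 28 by n − 14:

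| Evaluable n | Alpha | Power |
|---|---|---|
| 42 | 0.098 | 0.857 |
| 41 | 0.090 | 0.849 |
| 40 | 0.083 | 0.840 |
| 38 | 0.068 | 0.817 |

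(b) Lost patients stay among the 42 and count as non-responders. Replace p by p(1 − f), where f is the share lost:

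| f | Power |
|---|---|
| 1/46 | 0.843 |
| 2/46 | 0.827 |
| 4/46 | 0.79 |

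(c) Interim look at p1. The chance of stopping is 0.75^14 + 14 × 0.25 × 0.75^13 = 0.101. If one of the 14 is missing and counted as a failure, it is 0.75^13 + 13 × 0.25 × 0.75^12 = 0.127.

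**The case against.** The case for the rule has real support.

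- **Samples are part of the design.** Willingness to give them is an entry criterion, surgical tissue is mandatory, and the primary endpoint needs Ki67 from the surgical tumor. Ki67 also appears among the study tissue tests in 9.4.5 and 14.2. A sponsor may choose to make sampling a condition of participation. The consent form is not among the documents reviewed, so its wording cannot be checked.
- **A reader might infer that 4.6.3 flatly contradicts 4.6.2 and 9.4.5.** The documents do not go that far. The three items in 4.6.2 are put to a patient who is already withdrawing, and 4.6.3 can be read as the specific rule for samples. The PI's waivers cover fresh biopsies. They do not expressly cover correlative blood, archival tissue or surgical tissue, and a PI omitting a procedure is not a patient withdrawing consent. They weaken the stated reason without cancelling the rule.
- **A reader might also infer that her primary endpoint and safety follow-up are thrown away.** Section 4.6.3 ends further participation only, and the table above shows what is kept.
- **The power loss is small** and rests on assumed counts.

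These points limit the claim. They do not explain why a patient willing to be followed should be lost to recurrence and safety recording, or how 4.6.3 fits the statements covering all subjects in 4.6.1 and all patients in 10.2.

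**Conclusion.** The point holds as an inconsistency that creates avoidable missing data. The text ends study observation for a patient who may object only to research use of her samples, and its stated reason is weakened by the discretion to omit fresh biopsies. The important case is withdrawal before surgery, where mPEPI and pCR go uncollected and the remaining safety window goes unrecorded, with no replacement in the expansion phase.

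The numerical effect is small unless such withdrawals are common. If lost patients are non-evaluable, one or two beyond the four-place allowance cost about 1 to 2 points of power. If they count as non-responders, 2 of 46 bring power to 0.83 and 4 of 46 to 0.79. Which model applies depends on a rule for missing mPEPI that the plan does not give. This is a cheap improvement and not a flaw in the design, whose operating characteristics reproduce.

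**What to change.** Amend 4.6.3 so that sample-only withdrawal leads to destruction of stored research samples and no further research sampling. State that standard-of-care surgical pathology for mPEPI and pCR, AE/SAE recording and recurrence follow-up continue unless she separately withdraws those under 4.6.2. Remove the sentence that turns sample withdrawal into study withdrawal.

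Two clarifications must go with it:

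1. State whether the Ki67 used for mPEPI (8.2, footnote 15) is a clinical pathology result or is run on donated tissue (9.4.5, 14.2). If it is run on donated tissue, separating the consents does not by itself protect the primary endpoint.
2. Reconcile 4.6.1, 4.6.2 and 4.6.3 on study treatment after sample-only withdrawal. The documents now stop it through withdrawal from participation. That rule is for the investigators and the sponsor to settle, and this point does not propose one.

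The cost is a short amendment and matching consent wording. Some patients will lack exploratory samples, as the discretion over fresh biopsies already allows.
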